6.2.2.2 Overdose

The effect of overdose of this product are not known.

6.2.3 Dose Escalation, Stopping Rules and Dose-limiting Toxicities (DLTs)

The preliminary estimate of MTD will use BLRM design. Refer to [Section 10.2](#) for further details of stopping rules.

A DLT will be defined as any of the following occurring in a subject during the DLT period (first [REDACTED] treatment days for both AMG 596 monotherapy and in combination with AMG 404) and regarded to be related to AMG 596 and/or AMG 404. For adverse event severity grading see [Section 9.2](#) (Adverse Events). The Common Terminology Criteria for Adverse Events (**CTCAE version 4.0**) will be used to assess toxicities/adverse events with the exception of cytokine-release syndrome (CRS) with grading performed according to the recommendations provided in [Appendix E](#).

Hematological DLTs

- ANC < $0.5 \times 10^9/L$ for ≥ 7 days
- Febrile neutropenia (fever of unknown origin without clinically or microbiologically documented infection) with ANC < $0.5 \times 10^9/L$ and fever $\geq 38.5^\circ C$

- Platelets $< 50 \times 10^9/L > 7$ days or clinically significant bleeding
- Lymphopenia of any grade is not considered a DLT

Non-hematological DLTs

- Any grade 4 non-hematological toxicity
 - Laboratory parameters of grade ≥ 3 , not considered clinically relevant, and improved to grade ≤ 2 within 72 hours will not be considered DLT (for ALT and GGT elevations grade ≥ 3 , not considered clinically relevant, and improved to grade ≤ 2 within 7 days due to the long half-life of these parameters)
- Any grade 3 or higher non-hematological toxicity if:
 - Nausea and vomiting, which is refractory to anti-emetics
 - Flare-up of pain because of potential increase in tumor volume is not regarded as a DLT
 - Grade 3 non-hematologic toxicity lasting > 3 days despite appropriate treatment
 - Grade 3 fatigue will not be classified as DLT, irrespective of duration
 - Grade 3 acute kidney injury
 - Any grade 3 seizure, ataxia or encephalopathy
 - Other grade 3 neurologic-related adverse events lasting > 3 days despite appropriate treatment
 - Neurologic-related adverse event leading to treatment interruption that needed more than 1 week to resolve to CTCAE grade ≤ 1
 - Any grade 3 endocrinopathy that cannot be adequately controlled by hormonal replacement

Any adverse event occurring outside the DLT window that is determined by the investigator to be possibly related to the investigational product, which is seen more frequently or more severe than expected or is persistent despite appropriate management, can be determined to be a DLT upon unanimous decision by the DLRT after review of the adverse event and all available safety data.

The dosing schedule is described by a schema in the protocol synopsis.

6.2.4 Dosage Adjustments, Delays, Rules for Withholding or Restarting, Permanent Discontinuation

6.2.4.1 AMG 596

Dose Delay or Dose Reduction

Any clinically relevant (as determined by the investigator) grade 4 adverse event related to IP that does not meet the DLT criteria should lead to a dose delay and/or a dose reduction. The decision if a dose delay or reduction will be performed is up to the investigator's discretion. The sponsor may be consulted.

In addition, cytokine release syndrome of \geq grade 3 ([Appendix E](#)) should lead to dosing interruption and treatment with immunosuppressive therapies should be performed (see [Section 6.3](#) for details).

In case of re-appearance of the same grade 4 adverse event, IP should be permanently discontinued.

For persistent or re-occurring clinically relevant grade 3 adverse event related to IP, a dose delay or a dose reduction should be considered.

Infusion Interruption

Significant events requiring a change in treatment will be managed by immediate infusion interruption and should be documented in source documents and in the eCRF:

- The subject experiences a DLT as defined in [Section 6.2.3](#).
- The subject experiences a clinically relevant grade 4 adverse event related to IP (see above)
- The subject meets criteria for discontinuation of IP as described in [Section 8.3](#)
- Technical problem with the infusion pump
- The investigational product is incorrectly prepared or administered (eg, overdose)

Restarting the Infusion

Treatment may resume if the interruption is \leq 21 days:

- If the interruption occurred due to other reasons than toxicity (technical or logistic reasons; eg, diagnostic measurements). The infusion can be restarted at the same dose and without additional measures or delays.
- The toxicity has resolved to \leq grade 1. The infusion can be restarted according to guidelines presented in [Table 3](#) and [Table 4](#). Non-hematological Criteria for Dose Reduction.
- The toxicity occurred during the DLT period and has resolved to grade 2. The infusion can only be restarted in an individual subject with a clear clinical benefit from treatment after consultation with the sponsor on a case-by-case basis.

Restarting the infusion after a treatment interruption requires care and should be performed in the clinic/hospital under the supervision of the investigator or designee and the subject should be hospitalized for a minimum of 24 hours when the infusion interruption meets the following criteria:

- associated to an AE, or
- interruption > 24 hours due to a pump related issue.

The restart should be performed in the hospital with all infusion day 1 specific measures if the reason for the interruption was other than a technical issue (eg, pump related

issue) or the interruption was > 24 hours independent of reason. Prophylactic treatment with steroid (eg, dexamethasone) is mandated before restarting of AMG 596. If step-dosing was already performed at the start of a cycle, the infusion should be restarted with step-dosing again if the infusion interruption was [REDACTED].

Subjects in [REDACTED] that have a treatment interruption during cycle 1 should be allowed to complete a total of [REDACTED] infusion, and subjects in [REDACTED] cycles that have a treatment interruption during cycle 1 should be given the opportunity to complete a total of [REDACTED] of infusion even though these may not be DLT evaluable subjects. Replacement of subjects in [REDACTED] off schedule cohorts that have a treatment interruption during cycle 1 will require discussion on a case by case basis between sponsor and investigator.

Restart after an interruption lasting [REDACTED] may be allowed after careful risk-benefit evaluation and requires discussion between investigator and sponsor. Hematological criteria for dose reduction are presented in Table 3 and non-hematological criteria are presented in Table 4. Dose reduction is possible with re-treatment at 1 dose level lower (Section 6.2.4.1)

Table 3. Hematological Criteria for Dose Reduction

| CTCAE Grade | ANC (10 ⁹ /L) | Platelets (10 ⁹ /L) | Dose Delay ^a | Dose Reduction |
|---------------|--------------------------|--------------------------------|--|---|
| Hematological | | | | |
| 0-2 | > 1.0 | > 50 | Continue infusion | No change |
| 3 | < 1.0 – 0.5 | < 50 – 25 | Continue infusion until Investigator assesses toxicity to require interruption | No change |
| 4 | < 0.5 | < 25 | Delay until ≤ grade 2 | Restart at 1 dose level lower, consider re-escalation if completely recovered to baseline and no new toxicity occurred within 7 days of infusion. |

Approved

Table 4. Non-hematological Criteria for Dose Reduction

| CTCAE Grade* | Dose Delay | Dose Reduction | Comment |
|---|-----------------------|---|---|
| Non-hematological | | | |
| Cytokine release syndrome, tumor lysis syndrome, acute kidney injury | | | |
| 2 | Delay until ≤ grade 1 | No change | Restart in hospital |
| 3 | Delay until ≤ grade 1 | Restart at 1 dose level lower | Consider re-escalation if completely recovered and no new toxicity occurred within 7 days of infusion. Permanent discontinuation of study treatment if no recovery within 21 days. Start at the same dose if resolved cytokine release syndrome, infection, tumor lysis syndrome, or hypoxia. |
| 4 | Discontinue infusion | Permanent discontinuation of study treatment | - |
| All other non-hematological toxicities and clinically significant laboratory parameters | | | |
| 0-2 | Continue infusion | No change | Interruption can be considered if deemed necessary by the investigator |
| 3 | Delay until ≤ grade 2 | Resolution to grade 1 or 2: Restart at 1 dose level lower Resolution to normal within 1 week or a relationship to study drug can be ruled out: No change | Per the Investigator medical discretion to decide whether to continue the infusion for up to 72 hours if the toxicity or abnormal labs are responding to treatment or represents an asymptomatic laboratory change. Permanent discontinuation of study treatment if no recovery within 21 days |
| 4 | Discontinue infusion | Permanent discontinuation of study treatment | - |

ANC = Absolute neutrophil count; CTCAE = Common terminology criteria for adverse events;

DLT = Dose-limiting toxicity

^a Applies to all hematologic toxicity that persists for > 24 hours despite appropriate treatment

* For CRS criteria defined in [Appendix E](#) apply

Approved

6.2.4.2 AMG 404

Dose Delay or Dose Reduction

Each subject will stay on the dose level assigned until treatment needs to be stopped. The reason for dose withholds and dose delays is to be recorded on each subject's CRF. Specific guidance for management of adverse events associated with AMG 404 are provided in [Appendix G](#)

Immune-related Adverse Reactions

Adverse events following the administration of AMG 404 may represent an immunologic etiology. Based on clinical experience with other anti-PD-L1 therapies, these immune-related toxicities may occur shortly after the first dose to several months after the last dose of treatment and may affect more than one body system simultaneously. Early recognition and management are critical to reduce complications.

Most immune-related adverse events require adequate evaluation to confirm etiology or exclude other causes. Additional procedures or tests, such as bronchoscopy, endoscopy, or skin biopsy, may be included as part of the evaluation.

Based on the type and severity of the immune-related adverse event, withholding or permanent discontinuation of AMG 404 may be required, in addition to treatment with corticosteroids and/or other therapies. Dose modification and toxicity management guidelines for immune-related adverse reactions are provided in [Appendix G](#).

Infusion-related Reactions

Infusion-related reactions may occur with the administration of AMG 404. Monitor patients for signs and symptoms of infusion-related reactions, including pyrexia, chills, rigors, flushing, urticaria, hypotension, dyspnea, wheezing, headache, back pain, and abdominal pain. If an infusion-related reaction is suspected, perform a physical examination, monitor vital signs, monitor pulse oximetry, and perform an ECG if the patient is experiencing chest pain or sustained tachycardia.

For mild or moderate infusion-related reactions, interrupt or slow the rate of infusion. For severe or life-threatening infusion-related reactions, permanently discontinue AMG 404. Treatment guidelines for infusion reactions associated with the administration of AMG 404 are provided in [Appendix H](#).

Approved

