3.5 Treatment Schema

For treatment schema, pls. refer Figure 1 & Figure 2 from the protocol.

4. Covariates and Subgroups

Due to the small sample size, the impact of baseline characteristics on study outcomes will not be explored, and no subgroup analyses will be performed.

5. Definitions

Adverse Event (AE):

An adverse event is defined as any untoward medical occurrence in a clinical trial subject.

Dose Limiting Toxicity:

The grading of adverse events will be based on the guidelines provided in the common Terminology Criteria for Adverse Events (CTCAE) version 4.0 available online at <http://evs.nci.nih.gov/ftp1/CTCAE/About.html>).

Also, the grading for Cytokine Release Syndrome (CRS) will be performed according to the recommendations provided by [Lee et al, 2014](#) (Appendix E of the protocol).

A Dose Limiting Toxicity (DLT) is defined as any adverse event meeting the criteria listed below occurring during the first ■ days in each dose exploration cohort and attributable to AMG 596:

Hematological DLTs

- ANC < $0.5 \times 10^9/L$ for ≥ 7 days
- Febrile neutropenia (fever of unknown origin without clinically or microbiologically documented infection) with ANC < $0.5 \times 10^9/L$ and fever $\geq 38.5^\circ C$
- Platelets < $50 \times 10^9/L$ > 7 days or clinically significant bleeding

Non-hematological DLTs

- Any grade 4 non-hematological toxicity
- Any grade 3 or higher non-hematological toxicity if:
 - Nausea and vomiting, which is refractory to anti-emetics
 - Flare-up of pain because of potential increase in tumor volume is not regarded as a DLT
 - Grade 3 non-hematologic toxicity lasting > 3 days despite appropriate treatment
 - Grade 3 fatigue will not be classified as DLT, irrespective of duration
 - Grade 3 acute kidney injury
 - Any grade 3 seizure, ataxia or encephalopathy
 - Other grade 3 neurologic-related adverse events lasting > 3 days despite appropriate treatment
 - Neurologic-related adverse event leading to treatment interruption that needed more than 1 week to resolve to CTCAE grade \leq 1

Any adverse event occurring outside the DLT window that is determined by the investigator to be possibly related to the investigational product, which is seen more frequently or more severe than expected or is persistent despite appropriate management, can be determined to be a DLT upon unanimous decision by the DLRT after review of the adverse event and all available safety data.

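### For a first related grade 4 non-haematological event after the DLT period with no rule of its own, the Protocol 6.2.4.1 text says delay or reduce AMG 596, while Table 4 in the same section says stop

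*Protocol*

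**What the plan says.** The dose delay and reduction text of Protocol Section 6.2.4.1 says that every "grade 4 adverse event related to IP that does not meet the DLT criteria should lead to a dose delay and/or a dose reduction", provided that the investigator judges it clinically relevant. The choice between delay and reduction is left to the investigator, and consulting the sponsor is optional. The permanent stop comes later: "In case of re-appearance of the same grade 4 adverse event, IP should be permanently discontinued".

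The restart text of the same section applies once the toxicity is down to grade 1 or lower and the interruption has lasted no more than 21 days. It says "The infusion can be restarted according to guidelines presented in" Tables 3 and 4. A further bullet covers a different state: "The toxicity occurred during the DLT period and has resolved to grade 2". Restart is then possible case by case, for a subject with clear benefit and after consulting the sponsor.

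Table 3, for grade 4 haematological toxicity, says "Restart at 1 dose level lower, consider re-escalation if completely recovered to baseline", subject to no new toxicity. Table 4, for non-haematological toxicity, ends treatment permanently at grade 4 in both of its blocks. It makes no distinction between a first and a later event, and its comment cells at grade 4 are empty.

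Protocol Section 6.2.3 defines a DLT as a listed event "occurring in a subject during the DLT period" and related to study drug. A later event "can be determined to be a DLT upon unanimous decision by the DLRT". The SAP (Section 5, Dose Limiting Toxicity) words it differently: a DLT "is defined as any adverse event meeting the criteria listed below occurring during the first" days of a cohort, the number being redacted.

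**The concern.** Two rules in one section give different answers to the same bedside question: may this subject receive AMG 596 again? One site could delay, wait for recovery and restart at the same or a lower dose. Another would end treatment.

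This is a first-in-human study with safety as the primary endpoint, and Section 3.1 allows subjects to move to higher AMG 596 doses in later cycles, after the DLT period. The conditions are also uneven. Restart after a DLT under Section 6.2.5 needs recovery to grade 1 or baseline within 14 days, clinical benefit, agreement of the medical monitor and the subject's willingness. On the 6.2.4.1 text, a late grade 4 event that is not a DLT could be re-treated without the benefit or agreement conditions. Not every such event is life-threatening, since Table 4 also covers laboratory values. For those that are, the stopping rule should have one reading.

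**Working it through.** No arithmetic applies. The check is whether one event falls under both rules, and whether any text ranks them.

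1. **Inside the DLT period.** Section 6.2.3 lists every grade 4 non-haematological toxicity as a DLT. The exception is laboratory values not considered clinically relevant that improve within the stated time. The 6.2.4.1 text is limited to clinically relevant events, so it does not reach those values either. There is no overlap here.

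2. **After the DLT period.** The same event no longer falls in the DLT definition as 6.2.3 words it, because the period is part of that definition. It becomes a DLT only if the DLRT unanimously says so. Otherwise it is a clinically relevant, related grade 4 event that is not a DLT, and the 6.2.4.1 text applies. Table 4 carries no time limit, so it applies too.

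3. **Remove events with their own rules.** These are CRS (6.3.1, Appendix E), neurologic events (6.2.5, 6.3.2), acute kidney injury (6.2.5) and hepatotoxicity (6.3.3 to 6.3.6). AMG 404 handling (6.2.4.2, Appendices G and H) is also left aside. What remains is the catch-all block of Table 4.

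4. **Compare the instructions for a first event of this kind.**

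| | 6.2.4.1 text | Table 4 |
|---|---|---|
| Immediate action | Interrupt infusion | Stop infusion |
| After recovery | Delay and/or reduce, investigator decides | No restart |
| Permanent stop | Only if the same event recurs | At the first event |

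The immediate action is the same. The difference arises at restart.

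5. **Compare with haematological grade 4.** Table 3 says delay, then restart one level lower. That agrees with the 6.2.4.1 text, so the conflict is confined to non-haematological events.

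6. **Look for a sentence that ranks the two.** Section 6.2.5 lists DLTs, other unmanageable toxicity, and particular neurologic and renal events, but not grade 4 non-haematological events in general. The interruption list in 6.2.4.1 names DLTs and clinically relevant related grade 4 events as separate items. The second item points back to the delay/reduction text, and nothing limits that class to haematological events. The SAP contains no dose-modification rules beyond its CRS appendix. No precedence statement was found.

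**The case against.** The strongest reply is that the text can be read coherently. If *DLT criteria* means the severity list alone, without the time window, every clinically relevant grade 4 non-haematological event meets the criteria whenever it occurs. The 6.2.4.1 sentence is then left with haematological events, where Table 3 agrees with it. The SAP wording, which names the criteria and the window separately, supports this. Also, a site that follows the restart text is sent to Table 4, which offers no restart after grade 4, so re-exposure requires overlooking that step. And the affected class is narrow.

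All of this makes re-exposure less likely and shows which rule was probably intended. It does not settle the text. Protocol 6.2.3 builds the DLT period into the definition, and the 6.2.4.1 sentence covers any such event without a haematological limit. Following the restart reference also leaves the permission to delay or reduce with no effect for these events, and nothing says that this is meant.

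A reader might also infer that the bullet on toxicity resolved to grade 2 contradicts the grade 1 or baseline requirement of 6.2.5. The documents do not support that as a firm conflict. The bullet speaks of toxicity in the DLT period, not of DLTs, so it has scope of its own in non-DLT toxicity. It needs only a clarifying phrase.

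**Conclusion.** The inconsistency is real and should be corrected. For a clinically relevant, related grade 4 non-haematological event after the DLT period, with no event-specific rule and not declared a DLT by the DLRT, 6.2.4.1 says delay and/or reduce and stop on recurrence. Table 4 says stop at the first event. The wider text leans towards Table 4 without saying so. The conclusion rests on taking the DLT period as part of the DLT criteria, as the wording of 6.2.3 does.

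The number of subjects affected cannot be derived. A reader might infer a large effect because much of the 4 to 6 months of planned treatment (Section 3.4.1) follows the DLT period. But the length of that period is redacted, and a share of time is not a share of events. Nor do the 20% limit and the 10% to 30% rates in the expansion stopping rule (Section 10.2, Table 20) size it. Those are a monitoring limit and hypothetical rates, and they cover grade 4 or higher related events of every type. Nor do the documents support saying that sites will re-treat after such events, because the restart text refers them to Table 4.

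**What to change.** In 6.2.4.1, limit the delay/reduction sentence and the re-appearance sentence to haematological grade 4 events, in line with Table 3. Add that Table 4 governs AMG 596 for grade 4 non-haematological events inside or outside the DLT period, except where 6.2.5 (including its DLT restart conditions), 6.3 or Appendix E gives a specific rule.

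As a minor addition, state that the bullet on toxicity resolved to grade 2 applies to non-DLT toxicity, and that restart after a DLT follows 6.2.5 (grade 1 or lower, or baseline, within 14 days).

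Leave AMG 404 handling unchanged. A new statement keeping AMG 404 on its own schedule after AMG 596 has stopped could leave it given alone, a regimen that no arm describes.

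The cost is a protocol amendment with ethics committee approval (Section 12.1). The investigator also loses discretion to re-treat after a first grade 4 non-haematological event. Sample size, visits and analyses do not change.

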- For additional 72 hours after AMG 596 step dose if necessary

Cycle 2 and all subsequent cycles:

- For at least the first 72 hours of AMG 596 infusion in both Arm 1 and Arm 2
- For additional 72 hours after AMG 596 step dose if necessary.

Hospitalization may be shortened to 48 hours from the 6th cycle onwards at the discretion of the investigator.

AMG 404 can be administered in an outpatient setting starting from cycle 1 [REDACTED] onwards. Subjects should be monitored intensely in hospital or outpatient clinic for at least 4 hours after start of each AMG 404 infusion from cycle 1 [REDACTED] onwards.

Restart of infusion should be performed in the clinic/hospital under the supervision of the investigator or designee and the subject should be hospitalized for a minimum of 24 hours when the infusion interruption meets the following criteria:

- associated to an AE, or
- interruption > 24 hours due to a pump related issue.

Dosing with AMG 596 or the combination of AMG 596 and AMG 404 can continue unless the subject becomes intolerant to investigational product, the signs and symptoms of clinical progression are evident as determined by the investigator, or the subject withdraws consent. Tumor evaluations by MRI will occur every 10 to 12 weeks from treatment initiation. Earlier assessments can be made if clinically indicated at the discretion of the investigator. Modified RANO criteria will be used allowing subjects to stay on study until discontinuation criteria are met. Upon discussion with the Sponsor, subjects may continue to receive treatment beyond

radiographic confirmation of progressive disease as long as they continue to derive clinical benefit and until further increase in tumor burden. For analyses purpose, date of progressive disease (PD) is the date of initial observed clinical or radiographic PD.

Assessments during the course of the study include: Clinical evaluation (physical examination, Eastern Cooperative Oncology Group [ECOG] status, height, and weight), vital signs, pulse oximetry, neurological evaluation, electrocardiogram (ECG) triplicate measurement, laboratory assessments (including serum pregnancy test, if applicable, coagulation, hematology, chemistry, urinalysis, hepatitis serology, human immunodeficiency virus (HIV) test, [REDACTED])

[REDACTED] For a full list of study procedures, including the timing of each procedure, please refer to [Section 7](#) and the [Section 7.1](#) Schedule of Assessment.

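### Protocol 6.2.4.1 lets infusions stopped for non-toxicity reasons restart with no extra measures, but also requires steroid and, in many cases, a hospital restart

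*Protocol*

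**What the plan says.** All the text is in the current protocol, and none of it depends on redacted words.

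- **Permissive rule (6.2.4.1).** The paragraph opens "Treatment may resume if the interruption is" 21 days or less. One of its bullets covers stops "due to other reasons than toxicity (technical or logistic reasons; eg, diagnostic measurements"). For those: "The infusion can be restarted at the same dose and without additional measures or delays".
- **Hospital-stay list (6.2.4.1, next paragraph).** "Restarting the infusion after a treatment interruption requires care and should be performed in the clinic/hospital", with at least 24 hours in hospital, when the stop was linked to an adverse event or was a pump problem lasting more than 24 hours.
- **Day 1 rule (6.2.4.1, paragraph after that list).** The restart should be in hospital with "all infusion day 1 specific measures if the reason for the interruption was other than a technical issue", or if the stop lasted more than "24 hours independent of reason".
- **Steroid rule (6.2.4.1, same paragraph).** "Prophylactic treatment with steroid (eg, dexamethasone) is mandated before restarting of AMG 596". Sections 6.2.1.1, 6.3.2 (depressed level of consciousness) and 6.5 state the same mandate.
- **Repeats of the hospital-stay list.** The synopsis (Procedures) says "Restart of infusion should be performed in the clinic/hospital under the supervision of the investigator or designee" and gives the same two triggers, as does 7.2.2. Section 6.2.1.3 repeats the pump trigger.

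**The concern.** The permissive rule and the day 1 and steroid rules cover the same restarts and tell the site to do different things. Steroid here is a safety premedication: 6.2.1.1 attributes depressed consciousness to peritumoral edema caused by AMG 596 and says that dexamethasone can prevent it. A site that stops at the permissive sentence could leave the steroid out. It could also restart an outpatient after a logistic gap of several days without hospital supervision.

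Other sections send sites here. Section 7.3.13 holds drug after a positive pregnancy test and, if the confirmatory test is negative, restarts under 6.2.4. That hold is neither toxicity nor a technical fault, and 6.2.4.1 does not say which rule it follows.

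**Working it through.** No arithmetic applies. The check is to take each kind of stop named by the permissive rule, with the 24-hour cut-off from the day 1 rule, and read off what each text requires. The layout is mine; the protocol does not define these categories.

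| Stop | Permissive rule | Day 1 rule | Steroid mandate | Result |
|---|---|---|---|---|
| Technical, over 24 hours to 21 days | Same dose, nothing further | Hospital and day 1 measures, by duration | Applies | Conflict on setting and steroid |
| Logistic, over 24 hours to 21 days | Same dose, nothing further | Hospital and day 1 measures, by duration | Applies | Conflict on setting and steroid |
| Technical, 24 hours or less | Same dose, nothing further | Not triggered | Applies as written | Conflict on steroid only |
| Logistic, 24 hours or less | Same dose, nothing further | Depends on whether the stop counts as technical | Applies as written | Conflict on steroid; setting unclear |

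The last row turns on vocabulary. The permissive rule groups technical with logistic reasons. The day 1 rule speaks only of a technical issue, with a pump problem as its example, and does not say whether a logistic stop belongs there.

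The hospital-stay lists do not settle it. The lists in the synopsis, 6.2.4.1 and 7.2.2 name only stops linked to adverse events and pump stops over 24 hours. Logistic stops appear in none of them, although the day 1 rule sends at least the longer ones to hospital.

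On which text should yield: the Amendment 5 log for section 6.2.4, used here only as evidence of intent, shows that steroid before restart was deliberately raised from a recommendation to a mandate. The permissive sentence is therefore the one to bring into line.

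**The case against.** The best defence is that the paragraphs are consecutive and do different jobs: the permissive bullet says when treatment may resume, and the text after it says how. Beside the other bullets in its list, which deal with recovery from toxicity, dose-reduction tables and sponsor consultation, the waiver could mean only that no dose reduction, recovery wait or consultation is needed. The sentence is also permissive, so a site that gives steroid and restarts in hospital breaches nothing.

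That lowers the severity but does not remove the conflict. The sentence expressly waives additional measures, carries no cross-reference to the stricter rules, and nothing says which text governs.

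Two narrower objections carry weight.

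- The hospital-stay lists set a minimum stay, while the day 1 rule sets the conduct of the restart, so different triggers are not in themselves an error. Their silence on logistic stops makes misreading easier but is not a separate contradiction.
- The steroid sentence in 6.2.4.1 directly follows the day 1 rule, and those in 6.3.2 and 6.5 sit among, or refer to, text on cytokine release and neurologic events. The sponsor may not have meant to catch a brief pump stop. As written, however, no exception is stated.

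A reader might also infer three stronger points that the documents do not support.

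- **Most interruptions are affected.** The protocol gives no frequency of stops by reason or duration. Holds outside the technical and logistic labels, such as medication error (partly covered in 6.2.1.2) and the pregnancy-test hold, also mean that no tally of categories is complete.
- **Drug washout makes a late restart equivalent to a new start.** Section 2.5.3.1 gives a predicted half-life and refers the reader to the Investigator's Brochure for clinical data. No passage ties restart risk to serum level.
- **Section 6.3.1 under-doses dexamethasone.** Its 4 to 8 mg range includes the mandated 8 mg, it describes a recommended schema after cytokine release with added doses, and the mandate in 6.2.1.1, 6.3.2 and 6.5 governs.

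**Conclusion.** Section 6.2.4.1 is internally inconsistent on restarting AMG 596 after non-toxicity stops and needs correction. The conflict on hospital restart and day 1 measures is definite for every stop over 24 hours. The steroid conflict applies to every non-toxicity stop, on the plain reading that a mandate without a stated exception has none. For logistic stops of 24 hours or less, the hospital question stays open because the term that decides it is undefined.

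Severity is minor. The number of restarts affected is unknown, the documents report no harm from this wording, and a cautious site can satisfy every passage. No endpoint, error rate or sample size changes. The reason to act is that the text touches a safety premedication and the correction is nearly free.

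**What to change.** In the next amendment:

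1. In 6.2.4.1, limit the permissive sentence to technical stops of 24 hours or less. Reword it to say that the infusion restarts at the same dose with the mandated steroid prophylaxis, and that all other non-toxicity stops follow the hospital and day 1 rule below. If brief technical stops are meant to be exempt from steroid, write that exception into 6.2.1.1, 6.2.4.1, 6.3.2 and 6.5 instead.
2. State which rule covers logistic stops of 24 hours or less, and which covers other non-toxicity holds such as a false-positive pregnancy test.
3. Use the same categories in the restart lists in the synopsis, 6.2.4.1 and 7.2.2.
4. Give the steroid dose for restarts where day 1 measures do not apply. The restart passages name dexamethasone only as an example and state no dose, so the sponsor should choose it.

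The cost is wording only: no new data, analyses or subjects.
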